8.3 MELITAC 12.1

8.3.1 Product Description

The MELITAC 12.1 vaccine has 3 components: 12-MP peptides, Peptide-tet, and Montanide ISA-51 VG vaccine adjuvant, which will be prepared together as an emulsion for administration.

12-MP is a multipeptide mixture containing 12 class I MHC-restricted peptides derived from melanocyte differentiation proteins (MDP) and cancer testis antigens (CTA). The 12 peptides included in the vaccine are restricted to HLA-A1, -A2, or -A3 (Table 8.3.1.1).

Table 8.3.1.1. 12-MP Peptides

Allele	Sequence	Epitope
HLA-A1	DAEKSDICTDEY	Tyrosinase ₂₄₀₋₂₅₁ *
	SSDYVIPIGTY	Tyrosinase ₁₄₆₋₅₆
	EADPTGHSY	MAGE-A1 ₁₆₁₋₁₆₉
	EVDPIGHLY	MAGE-A3 ₁₆₈₋₁₇₆
HLA-A2	YMDGTMSQV	Tyrosinase ₃₆₉₋₃₇₇ ♦
	IMDQVPFPSV	gp100 ₂₀₉₋₂₁₇ #
	YLEPGPVTA	gp100 ₂₈₀₋₂₈₈

	GLYDGMEHL	MAGE-A10 ₂₅₄₋₂₆₂
HLA-A3	ALLAVGATK	gp100 ₁₇₋₂₅
	LIYRRRLMK	gp100 ₆₁₄₋₆₂₂
	SLFRAVITK	MAGE-A1 ₉₆₋₁₀₄
	ASGPGGGAPR	NY-ESO-1 ₅₃₋₆₂

* (substitution of S for C at residue 244)

◆ (post-translational change of N to D at residue 371)

(209-2M, substitution of M for T at position 210)

Peptide-tet is a slightly modified form of a 15 residue peptide p2 of tetanus toxoid (QYIKANSKFIGITEL), representing amino acid residues 830-844. This peptide binds to HLA-DR1, DRw15(2), DRw18(3), DR4Dw4, DRw11(5), DRw13(w6), DR7, DRw8, DR9, DRw52a, and DRw52b, which account for 80–90% of the patient population. Because glutamine (Q) at the N-terminus can cyclize, giving rise to a slight change in molecular structure, we have prepared this peptide as a 16-residue species, where an alanine residue (A) has been added to the N-terminus. Thus, the sequence of the tetanus peptide used is AQYIKANSKFIGITEL (Table 8.3.1.2).

Table 8.3.1.2. Tetanus Toxoid-derived Helper Peptide

Allele	Sequence	Epitope
Binds to multiple class II alleles	AQYIKANSKFIGITEL	p2 ₈₃₀₋₈₄₄ **
All peptide preparations are lyophilized and stored in sterile vials sealed with a rubber stopper. The peptides are stored at $\leq -70^{\circ}\text{C}$ and protected from light. Each lot of peptide has met the lot release criteria for identity, purity, trifluoroacetic acid (TFA) content, potency, pyrogenicity, general safety, and sterility. Human studies investigating the pharmacokinetics and metabolism of the 12-MP and Peptide-tet vaccines have not been conducted.		

8.3.2 Agent Supply

8.3.2.1 12-MP

The 12-MP mixture is supplied in sterile single-use vials of lyophilized white powder containing a mixture of the 12 peptides and salts to buffer the solution once reconstituted. Each vial of 12-MP contains 150 μg each of the 12 melanoma peptides. All peptides are synthesized under GMP conditions by Multiple Peptide Systems (San Diego, CA). The peptides were vialed under GMP conditions by Clinalfa Line (Merck Biosciences AG, Laufelfingen, Switzerland). These 12-MP vials are provided by the University of Virginia. The University of Virginia will be the distributor of the agent to the research sites.

8.3.2.2 Peptide-tet

Peptide-tet is supplied in sterile single-use vials of white powder. Each vial of Peptide-tet contains 300 μg of tetanus peptide. The peptide was synthesized under GMP conditions by Multiple Peptide Systems (San Diego, CA). The peptides were vialed under GMP conditions by Clinalfa Line (Merck Biosciences AG, Laufelfingen, Switzerland). The agent is provided by the University of Virginia. The University of Virginia will be the distributor of the agent to the research sites.

8.3.3 Solution Preparation

All vaccines are to be made in a certified, sterile laminar flow hood. The emulsion will be prepared as 3-mL quantities: 2 mL of this emulsion will be administered, with 1 mL of emulsion administered at each of 2 vaccine sites. At each site, half of each dose (0.5 mL) will be injected subcutaneously and half (0.5 mL) will be injected intradermally. The remaining 1 mL of the prepared emulsion is to be discarded.

The 2-mL dose of each vaccine contains 100 μ g each of the 12 peptides listed in [Table 1](#) of [Appendix E](#) and 200 μ g of tetanus peptide ([Table 2](#) of [Appendix E](#)), emulsified in 1 mL of Montanide ISA-51 VG adjuvant. See [Appendix E](#) for complete solution preparation instructions.

8.3.4 Storage Requirements

Vials of lyophilized peptides should be stored at \leq -70°C and protected from light. All peptide preparations are lyophilized and stored in sterile vials sealed with a rubber stopper. Each lot of peptide has met the lot release criteria for identity, purity, TFA content, potency, pyrogenicity, general safety, and sterility.

Ideally, vials of the 12-MP and Peptide-tet should be thawed just before preparing a vaccine (i.e., thawed at room temperature for 1–2 minutes before reconstitution). Repeated freeze-thaws should be avoided. Vials that are frozen and thawed >2 times should not be used. Vials should not be left at room temperature for more than 24 hours.

8.3.5 Stability

All peptide preparations will be assayed for stability at months 3, 6, 12, 24, and 36. High-performance liquid chromatography will be performed to confirm purity and sterility testing will be conducted in accord with FDA guidelines in 21 CFR, part 610.12. In addition, 1 vial of peptide will be submitted to either the Clinical Microbiology Laboratory at the University of Virginia or Microbiology Research Associates, Inc. (Acton, MA).

MELITAC 12.1 vaccine comprises 100 μ g each of the 12-MP mixture plus 190 μ g of Peptide-tet. Peptides are synthesized under GMP conditions by PolyPeptide Group (formerly Multiple Peptide Systems), reconstituted, mixed, sterile-filtered, and vialled under GMP conditions by Merck. The 12-melanoma peptide mixture and tetanus peptide preparation are made as separate sterile aqueous solutions to be administered in an emulsion with Montanide ISA-51 VG adjuvant (1 mL), using the 2-syringe method after emulsion stability and quality is verified.

After a peptide-based vaccine is mixed, the prepared vaccine should be refrigerated until just before administration. Ideally, the vaccine should be administered within 1–2 hours after mixing. The vaccine must be administered within 4 hours of mixing. If the vaccine is not administered within 4 hours of mixing, it should be discarded.

8.3.6 Route of Administration

All participants will receive 6 vaccination times over 12 weeks with MELITAC 12.1 (100 µg of each of 12 Class I MHC restricted melanoma peptides) ([Table 1](#) of [Appendix E](#)) and 200 µg of a tetanus helper peptide ([Table 2](#) of [Appendix E](#)) emulsified in Montanide ISA-51 VG adjuvant. In a given patient, half of the vaccine solution will be administered subcutaneously and half intradermally, once each week (vaccines 1–3), then once every 3 weeks (vaccines 4–6), in rotating skin locations on extremities clinically uninvolved with melanoma. For each vaccine, a total of 2 mL of emulsion will be delivered, which will consist of 1 mL of Montanide ISA-51 VG and the MELITAC 12.1 peptides. The vaccine dose will be divided and administered into 2 extremity sites uninvolved with melanoma (typically upper outer arm and/or upper lateral thigh).

At each injection site, a single needle puncture is to be performed, with delivery of 0.5 mL into the dermis and 0.5 mL into the subcutaneous tissue. This usually will require advancing the needle into the dermis, parallel with the skin surface, to deliver the first 0.5 mL, then pulling the needle back to near the skin puncture site, and advancing it into the subcutaneous tissue for delivery of the remaining 0.5 mL. For the dermal injections, it is acceptable to make several passes of the needle as the emulsion is delivered, where those needle passes are oriented radially from the needle puncture site.

8.4 Montanide ISA-51 VG

8.4.1 Product Description

The adjuvant Montanide ISA-51 VG has been used in a number of clinical trials with little toxicity observed. The possible side effects of receiving Montanide VG adjuvant include anaphylaxis in response to one of the ingredients (rare). Such a reaction might include hives, rash, generalized swelling of the body, hypotension, dyspnea, and abdominal pain, and possibly death.

8.4.2 How Supplied

Montanide ISA-51 VG is supplied in a glass container as a sterile, clear, pale yellow liquid by Seppic, Inc. (Fairfield, NJ). It is commercially available from Seppic, Inc., and will be distributed by the University of Virginia.

8.4.3 Solution Preparation

The vaccine adjuvant Montanide ISA-51 VG is prepared as a GMP-grade agent, in single-use glass vials or ampules. Refer to [Appendix E](#) for complete vaccine preparation instructions.

8.4.4 Storage Conditions

Montanide ISA-51 VG should be stored at room temperature.

8.4.5 **Stability**

An expiration date for Montanide ISA-51 VG is provided by Seppic, Inc., and the drug should not be used beyond this date.

8.4.6 **Route of Administration**

Refer to [Appendix E](#) for complete vaccine preparation instructions.

8.5 **Commerical Agent: N/A**

9. BIOMARKER, CORRELATIVE, AND SPECIAL STUDIES

9.1 **Biomarker Studies**

9.1.1 **Collection of Specimens**

9.1.1.1 **Fine-Needle Aspiration (FNA) Biopsy of Tumor**

FNA biopsy will be prepared as detailed below and stored frozen in liquid nitrogen.

9.1.1.2 **Tumor Biopsies**

Biopsy specimens must include at least 100 mm³ of tumor tissue and ideally 1 cm³ or more. The specimens may be obtained by excisional biopsy, incisional biopsy, or core biopsy. Each surgical specimen or set of core biopsies will be divided into 5 portions: 1/4th will be placed in RPMI and will be processed to yield cryopreserved viable cells for flow cytometric analysis, 1/4th will be fixed in formalin and then embedded in paraffin for histology, 1/6th will be flash frozen in OCT for histology, 1/6th will be flash frozen without medium for Kyn/Trp ratio and 1/6th will be flash frozen in RNA Later for gene expression. (See Laboratory Manual for additional information).

If an archived pre-treatment biopsy is obtained from a formalin-fixed paraffin-embedded (FFPE) tissue block, there must be at least 20 slides available for study.

9.1.1.3 **Blood**

Blood will be collected for serum and PBMC isolation as designated below.

9.1.2 **Processing and Shipping of Specimen(s)**

Tumor specimens will be collected as described above, at the bedside when tumor is biopsied. They will then be processed and shipped as specified below.

9.1.2.1 **Portion for single-cell suspensions**

This will be submitted to mechanical dissociation then, as appropriate, enzymatic digestion (typically collagenase, DNAase, and hyaluronidase). The resulting cells will be collected by centrifugation and cryopreserved viably in 10% dimethyl sulfoxide (DMSO) and either 12.5% HSA (Human serum albumin or 12.5% FCS (Fetal calf serum) using a

controlled-rate freezer. Samples will be stored at -80°C and then batch-shipped on dry ice to the CITN Central Laboratory.

9.1.2.2 Portion for Formalin Fixation

These will be placed in formalin, and shipped (ambient) overnight to the CITN Central Laboratory. After adequate fixation, samples will be embedded in paraffin and formalin-fixed paraffin embedded (FFPE) blocks stored at room temperature.

9.1.2.3 Portion for Quick-Freezing in OCT

This will be placed in OCT at the patient bedside and placed immediately onto dry-ice for hardening. Samples will be stored at -80°C and then batch-shipped on dry ice to the CITN Central Laboratory.

9.1.2.4 Portion for Quick-Freezing Without Media

This will be placed in a cryovial and placed immediately into liquid nitrogen for flash freezing. Samples will be stored at -80°C or in liquid nitrogen and then batch-shipped on dry ice to the CITN Central Laboratory.

9.1.2.5 Blood Samples

- A) Blood in red-top (or comparable) tubes for serum isolation and green-top tubes for plasma isolation, and CPT tubes (for RNA isolation) will be processed locally, aliquoted into cryovials, and frozen at -80°C. They will be batch-shipped on dry ice to the CITN Central Laboratory.
- B) Blood in green-top (or comparable) tubes for PBMC isolation and CellSave Preservation tubes will be shipped at ambient temperature in insulated containers to the CITN central laboratory at the University of Washington.

9.1.3 Shipping of Specimens

Fresh blood collected for PBMC isolation will be shipped at ambient temperature overnight in insulated containers to the CITN central laboratory. Biopsy specimens in formalin will be shipped with the green top tubes to the CITN Central Laboratory for paraffin embedding as described above. (FFPE) tumor biopsies will be stored at room temperature, then shipped in batch periodically to the University of Virginia ([name] laboratory) for analysis. FNA biopsies will be stored in liquid nitrogen or at -80°C, then shipped in batch to the CITN Central Laboratory for later batch shipment to the laboratory of Drs. [name] and [name] for analyses. Frozen serum, plasma and viably frozen tumor cells and frozen tumor tissue will be shipped in batch to the CITN Central Laboratory on dry ice for same day or overnight delivery.

9.2 Laboratory Correlative Studies

9.2.1 Immunohistochemical Evaluation of Tumor Biopsies - Laboratory Correlative Study #1

Tumors will be assessed by IHC for pattern of T-cell distribution and infiltration of cells expressing a variety of antigens including CD3, CD4, CD8, CD56, CD34, CD45, CD20, CD138, CD163, DC-LAMP, FoxP3, PD-1, and IDO1, as well as PD-L1 on tumors. The primary endpoint of the trial will be a change in the number of CD8+ cells infiltrating tumor (per mm²) comparing pre- and post-treatment biopsies for each patient. We will use the assessment of total CD3+ T cells and total CD45+ lymphocytes as confirmatory assays. IHC staining will also be performed to detect other key parameters including IDO1 expression, and presence and patterns of CD4+ T cell and FoxP3+ Treg infiltration. These antibodies all work in FFPE tissue sections.

Tissue sections will be processed with heat-induced antigen retrieval and stained as described [[Erdag 2012](#)], using antibodies to CD4, CD8, NKp46, CD31, CD45, CD20, CD3, CD138, CD163, DC-LAMP, FoxP3, PD-1, and IDO1. EnVision™ System (enzyme-conjugated polymer backbone coupled to secondary antibodies) and 3,30-diaminobenzidine chromogen (Dako North America, Inc., Carpinteria, CA) will be applied to develop the staining. Positive controls for lymphocyte antibodies will include lymph node and for CD34 antibody, placenta. Negative control slides will use phosphate buffered saline instead of primary antibody, with other conditions held constant.

If the tumor specimen is too small for evaluation of all antigens, the priority will be CD8 > CD3 > IDO > CD31 > CD45 > FoxP3 > remainder. Stained sections will be reviewed for type, density, and location of tumor-infiltrating immune cells, tumor cell type, necrosis, hemorrhage, and melanin pigment. At least 5 high-powered fields will be examined. Fields with no tumor tissue, more than 50% necrosis, or hemorrhage will be excluded. Stained cells will be enumerated by a single pathologist on each core in a high-power microscope field, excluding cells within blood vessels or in hemorrhagic or necrotic areas. Cell counts will be normalized to per mm². Alternatively, when automated image analysis software is available and validated, it may be used for quantification of the staining. Change in the number of tumor-infiltrating lymphocytes will be analyzed using standard descriptive statistical analyses described below.

Immunotypes will be defined by staining for immune cells (CD45) and for intratumoral blood vessels (CD31) as described [[Erdag 2012](#)].

Additional histologic studies may be performed as appropriate to elucidate the immunologic changes in the tumor specimens. If IHC studies are needed using antibodies that do not work well in FFPE sections, or for immunofluorescence studies, one of the quick-frozen tissue samples will be used for those purposes.

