9.2.5.2 Handling of Specimen(s)

Blood samples will be processed locally, and frozen aliquots shipped to the CITN Central Laboratory. The Central Laboratory will distribute aliquots to Incyte where testing will be done in a blinded fashion.

Biopsy specimens will be collected and stored at -80°C (if frozen) at the collection site.

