12.3 Collaborative Agreements Language – N/A

13. STATISTICAL CONSIDERATIONS

13.1 Study Design/Endpoints

The proposed study is a Phase II, open label, multicenter study of the administration of INCB024360, an IDO1 inhibitor, plus a multipeptide melanoma vaccine, MELITAC 12.1, in patients with advanced (i.e., surgically incurable stage III or IV) melanoma having tissue amenable to serial biopsy.

The first 3 patients will be administered the INCB024360 in a reduced amount of 300 mg bid and enrolled in a staggered design with a 2-week waiting period between each of the first 3 patients ([Table 5.1](#)). This is a safety precaution due to unknown effects of the combination of INCB024360 with the multipeptide melanoma vaccine. Although both agents have excellent safety profiles, unexpected toxicities could occur when used together.

Each patient's tumor(s) will be biopsied before therapy and during therapy to assess the effects of INCB024360 and vaccine by IHC and transcriptome analysis ([Table 5.1](#)).

INCB024360 is expected to normalize serum Kyn/Trp ratios, in turn altering the tumor microenvironment, which includes the number and character of tumor-infiltrating T cells. The addition of MELITAC 12.1, a multipeptide melanoma vaccine, will be used to compare INCB024360 alone and with the vaccine. Effects of IDO inhibition on systemic vaccine-induced immunity will be assessed by evaluating peripheral blood immune responses to the MELITAC 12.1 vaccine. The comparator for immune responses will be taken from published experience with similar patients treated with the same vaccine regimen but without INCB024360 [[[name] 2011](#); [[name] 2009](#)].

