13.2 Primary Endpoint

Published data on immune cell infiltration of melanoma metastases showed that amongst 148 metastases, CD8 T cells ranged from 0 to 592 per mm². The mean was 137, with standard deviation of 143; median 94 per mm². [Erdag, Cancer Research 2012]

The primary endpoint will be changes in the concentration and number of CD8+ cells infiltrating tumor pre- and post-treatment with each patient serving as their own control so that relative increases within each patient will be assessed. We will use the assessment of total CD3 T cells and total CD45 lymphocytes as confirmatory assays. Twelve patients should enable adequate power to discern large changes (e.g. increases of about 1 SD of the original data set.)

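### Section 9.2.1 lets the primary CD8+ count move from hand to software mid-trial without holding a patient's biopsies to one method, and no masking of the reader is specified

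*Combined protocol and SAP*

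**What the plan says.** Section 9.2.1 makes the change in CD8+ cells per mm² between pre- and post-treatment biopsies the primary endpoint. The default reading is manual: "Stained cells will be enumerated by a single pathologist on each core in a high-power microscope field". On field selection it says "At least 5 high-powered fields will be examined", and it excludes fields that lack tumor, are mostly necrotic or are hemorrhagic. It then permits a second method: "Alternatively, when automated image analysis software is available and validated, it may be used for quantification of the staining".

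Section 13.2 gives the comparison: "with each patient serving as their own control so that relative increases within each patient will be assessed". Section 13.1 describes the trial as open label and gives it no concurrent control for this endpoint. Section 5.1 sets two contrasts: pretreatment against day 21, and day 21 against day 42.

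The only blinding statement in the documents is in Section 9.2.5.2, for the Kyn/Trp assay: "testing will be done in a blinded fashion". Section 9.1.3 has paraffin-embedded biopsies "shipped in batch periodically to the University of Virginia", whereas Section 9.2.1.1 places the CD8 and CD3 evaluation at a different laboratory, in Seattle. Sections 2.4.4, 3.1.2, 5.1 and 9.1.1.2 allow archived tissue to stand in for the pretreatment biopsy.

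**The concern.** In an own-control design, the two readings that form a difference must be made the same way. The software clause is conditional on a date (when the software becomes available), so a switch would run from earlier reads to later ones. For any patient whose biopsies fall on both sides of it, the method change coincides with pre versus post treatment. No control arm is available to subtract it.

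Masking is a separate matter. Hand counting with a minimum number of fields, and no rule for which eligible fields to take, leaves room for judgment. If the reader knew which slide was pretreatment, that judgment could lean toward the hypothesis stated in Section 2.4, that infiltration increases. Unlike a method switch, this could touch every patient.

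What is at stake is the size of the CD8 change. Sections 1 and 11 make a substantial change at tumor sites the trigger for follow-on trials.

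**Working it through.** **The plan's own figure.** Section 13.2 cites a CD8 mean of 137 and SD of 143 per mm² and says that 12 patients give adequate power for an increase of about 1 SD. It gives no alpha, test, within-patient correlation or power, so there is no number to reproduce. Assuming a two-sided 5% paired t test and SD of change = 143 × √(2(1 − r)), the exact power for a 143 cells/mm² increase is:

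- r = 0: SD of change 202, power 61%
- r = 0.5: SD of change 143, power 88%
- r = 0.75: SD of change 101, power 99%

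**How many patients could straddle one switch date.** Assume slides are read as they arrive. The pretreatment biopsy may be taken up to 14 days before day 0 (Section 5.4), so pretreatment to day 21 spans 21 to 35 days. Day 21 to day 42 spans 21 days. Section 13.3 expects about 3 patients per month. Then 3 × 21/30.4 = 2.1 and 3 × 35/30.4 = 3.5, so roughly 2 to 4 patients straddle in a given contrast. I take 3 and 4 as the working cases.

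**Size of the shift.** Assume the methods differ by 20% to 50% at the cited mean: 0.20 × 137 = 27.4 and 0.50 × 137 = 68.5 cells/mm². Bias in the mean change = shift × (patients straddling)/12:

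- 3 of 12: 27.4 × 3/12 = 6.9; 68.5 × 3/12 = 17.1
- 4 of 12: 27.4 × 4/12 = 9.1; 68.5 × 4/12 = 22.8

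The bias is therefore about 7 to 23 cells/mm², or 5% to 16% of the 143 target (6.9/143 and 22.8/143). On a ratio scale, closer to Section 13.2's relative increases, the spurious rise in the geometric mean runs from 1.2^(3/12) = 1.05 to 1.5^(4/12) = 1.14.

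**Effect on a test.** With no true treatment effect, normal differences, n = 12 and a two-sided 5% paired t test, rejection rates are as follows (400,000 simulated trials for partial straddling; exact noncentral t when all 12 straddle):

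| Patients straddling | r = 0.5, shift 20% / 50% | r = 0.7, shift 20% / 50% |
|---|---|---|
| 3 | 5.2% / 6.0% | 5.3% / 6.8% |
| 4 | 5.4% / 7.3% | 5.6% / 8.7% |
| 6 | 6.0% / 10.7% | 6.5% / 14.2% |
| 12 | 9.3% / 32.9% | 12.3% / 49.8% |

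The row for 6 is a sensitivity case. If pre- versus post-treatment is taken as pretreatment to day 42, the span is 42 to 56 days, and 3 × 42/30.4 = 4.1 to 3 × 56/30.4 = 5.5 patients would straddle.

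**Can all 12 straddle?** At 3 per month, accrual takes 12/3 = 4 months, longer than any patient's 21 to 35 day gap. Section 5.1 slows it further by staggering the first three patients and then halting enrollment. One switch date cannot split every patient if slides are read on arrival. If a patient's slides are read together, none straddles. All 12 would straddle only if slides were read grouped by visit, which no section describes.

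No such calculation is possible for an unmasked reader, because the documents offer no basis for the size of that shift.

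**The case against.** The strongest reply is that safeguards exist and the likely effect is small. The software must be validated as well as available, one pathologist does the manual counting, and field exclusions are stated. The analysis is described as descriptive (Section 9.2.1) and the endpoint objectives as exploratory (Section 11), so no p-value is promised and the test-based figures are a construct of this review. With 3-4 patients straddling, the error rate barely moves.

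Much of this stands, and it limits the point to bias in the estimate. It does not remove it. Validated software can still count differently from a particular pathologist, and a single reader is not a masked reader.

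Three stronger readings might be inferred, and the documents do not support them:

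- **That the CD8 reader is unmasked.** The documents are silent. Section 9.1.1.2 refers to a Laboratory Manual that is not among them and might cover this. Only the permission to change method is written down.
- **That periodic batch shipping splits a patient's visits.** The batch text in Section 9.1.3 names the University of Virginia, while Section 9.2.1.1 puts CD8 at the Seattle laboratory. The batch text therefore does not establish how CD8 slides are handled, and batching could as easily bring visits together.
- **That false-positive rates reach 9-50%.** Those figures need all 12 patients to straddle the switch, which the enrollment pattern makes implausible if slides are read on arrival.

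**Conclusion.** The point holds as a gap in the measurement rules for the primary endpoint. The plan expressly permits a change of counting method, does not hold a patient's biopsies to one method, and specifies no masking of the CD8 reader to time point. With no control arm, any resulting shift goes into the estimated change.

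Under an assumed 20-50% method difference with 3-4 of 12 patients straddling one switch date, the bias is about 7-23 cells/mm², and an assumed paired t test at a nominal 5% rejects about 5-9% of the time. This rests on the assumed method difference, a correlation of 0.5-0.7, reading on arrival and the projected accrual rate. There is no bias from this source if no switch occurs or if each patient's slides are read together by one method. A shift from an unmasked reader would be additional and cannot be sized. The matter merits a change because the endpoint is primary and uncontrolled and the remedy is inexpensive, not because a false finding is likely.

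**What to change.** Add to Section 9.2.1:

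> All CD8 slides from a patient (pretreatment, including archived tissue; day 21; day 42) will be coded and read together in random order by the same pathologist, masked to time point, using one counting method. If validated image analysis is adopted, all slides already read will be re-quantified with it, and the primary analysis will use that one method throughout.

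Reconcile Sections 9.1.3 and 9.2.1.1 so that the route and laboratory for the CD8 slides are clear. If the Laboratory Manual already contains masking or same-session rules, cite them here.

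Cost: slides must be coded, reading waits for the patient's last biopsy, and a switch to software would mean re-quantifying at most about 12 × 3 = 36 existing slides. No extra reader, biopsy or patient is needed.
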